4.2 Duration of Study

The K07 training grant is a 5-year grant. The app development and refinement (Phase 1) will occur in years 1-2 and the pilot RCT (Phase 2) will occur in years 3-5.

Phase 1: App Development. We have planned for a period of 12-18 months for development, usability testing, and refinement. Information will be gathered from childhood cancer survivors about desired features of the app via interview. During development, feedback about the quality of the program and design elements will be sought. Once a usable app is developed, individuals will be asked to field test the app for a brief period (e.g., a few days or a week, depending on needs identified during development) to evaluate usability in a real-world setting prior to beginning Phase 2.

Phase 2: Pilot RCT. Recruitment will occur in waves, such that cohorts of 10-20 participants will be randomized simultaneously, and each arm will have 5-10 patients at a

time. Following individual consent/assent and completion of a baseline assessment, individuals will be randomized either to the Technology-Enhanced Intervention (TLC FIT) arm or the Waitlist Control (WLC) arm (see Figure 2). Individual data collection will last approximately 9 months, with assessments conducted at approximately 2, 3, 6, and 9 months following randomization. Individuals randomized to the waitlist will receive the intervention after the 6-month assessment. Recruitment and data collection for Phase 2 are expected to span two to three years.

Overview of Study Duration

Study Year	1→				2→				3→				4→				5→			
Quarter	1	2	3	4	1	2	3	4	1	2	3	4	1	2	3	4	1	2	3	4
Phase 1: App Development																				
Training in App Development																				
IRB & study prep																				
App development/Refinement																				
Phase 2: Pilot RCT																				
IRB & study prep																				
Recruitment																				
Data Collection																				
Data Analysis																				
Manuscript Prep																				
Write/Submit Grant																				

5. Patient Selection Criteria

5.1 Inclusion Criteria

Phase 1: A patient is eligible for enrollment if all of the following criteria are met:

- 5.1.1 Any diagnosis of cancer prior to age 21
- 5.1.2 Current age 13-25
- 5.1.3 Off treatment
- 5.1.4 For patients < 18 years, parents must give informed consent and patient must give assent. Patients ≥ 18 must give informed consent.

Phase 2: A patient is eligible for enrollment if all of the following criteria are met:

- 5.1.5 Any diagnosis of cancer prior to age 21
- 5.1.6 Current age 13-25
- 5.1.7 Off treatment for at least 6 months
- 5.1.8 For patients < 18 years, parents must give informed consent and patient must give assent. Patients ≥ 18 must give informed consent.

5.2 Exclusion Criteria

Phase 1: A patient is not eligible for enrollment if any of the following criteria are met:

- 5.2.1 Non-English speaking
- 5.2.2 Significant developmental delay per patient, parent, or physician report
- 5.2.3 Pregnant (per patient report)

Phase 2: A patient is not eligible for enrollment if any of the following criteria are met:

- 5.2.4 Any medical contraindication to exercise according to a physician or physician's designee
- 5.2.5 Non-English speaking
- 5.2.6 Current physical activity level exceeding CDC guidelines for activity (60 min of moderate-vigorous exercise/day for 5+ days/wk including 3+ days of vigorous intensity activities and muscle-strengthening exercises on 3+ days/wk and bone-strengthening exercises on 3+ days/wk for children <18 and 150 min of moderate-vigorous exercise or 75 min of vigorous exercise/wk and 2+ days of muscle-strengthening activities for adults \geq 18). The CDC guidelines are used to determine exercise prescription in our intervention; individuals already exceeding the guidelines would be unlikely to benefit from participating.
- 5.2.7 Significant developmental delay per patient, parent, or physician report
- 5.2.8 Pregnant (per patient report)
For Phase 2, if participant becomes pregnant during the course of the study, she will be removed from further participation

5.3 Inclusion of Women and Minorities

Males and females and members of all ethnic groups are eligible for this study. We expect the distribution of sex and race/ethnicity to reflect that of the Rutgers CINJ.

5.4 Participation of Children

This study includes children, as the primary goal is to evaluate an intervention specifically designed for adolescents and young adults ages 13-25. To protect children who are considered a vulnerable population, we will obtain both individual assent and parent consent for participation in the study for all children under the age of 18. We will also clearly explain and document that participation in the study in no way influences medical care. The PI and mentor, [name], have significant experience and expertise in working with children of this age range and their families. Co-Investigator [name] has experience conducting exercise interventions with children.

5.5 Sources or Methods of Recruitment

Patients will be recruited through the Rutgers CINJ LITE (Long-term, Information, Treatment effects, and Evaluation) program, which provides long-term evaluation, support, and health education for childhood cancer survivors, through their routine office visit or mail. Patients will also be recruited through physician or staff referral in the Division of Pediatric Hematology/Oncology. Patients will also be recruited through flyers posted or available in relevant places (e.g., community support centers for teens and young adults with cancer). Flyers will be posted in the LITE clinic space and advertisements will be posted in the Rutgers CINJ LITE newsletter to recruit; these materials will be submitted and approved by the IRB prior to use. We will make information about the study available via webpage, www.cinj.org/fitsurvivor. We will also post advertisements with a link to the study webpage or IRB-approved flyer on social media sites, including Facebook and Twitter. The study team will also periodically (approximately 4-6 times per year) hold informational meetings for potentially eligible participants to learn about the program and ask questions. Study

information will be sent to the faculty and staff via Rutgers email lists or online news media, such as the Faculty & Staff Bulletin and Rutgers Today or Research News.

5.6 Study Enrollment Procedures

For Phase 1, potential participants may be recruited during their Rutgers CINJ LITE office visit. The PI or trained study staff will approach potentially eligible patients and families to provide a brief description of the study, answer any questions, and obtain informed consent/parental permission and assent (for children 13-17). Participants will be given as much time as needed to read the consent/assent materials and ask any questions. [name], the Director of the Rutgers CINJ LITE program and a Co-Investigator on this study, and [name], LCSW, the primary social worker for the LITE program, will assist in recruiting by identifying potentially eligible patients from patient records. For those who are not due for a routine LITE visit, the study team will mail an invitation with an insert noting available interview dates and follow-up with a phone call to answer any questions and arrange for an in-person meeting to obtain consent/parental permission/assent and conduct the interview about desired features for the app. Phone calls can be made up to three times per week, with a maximum of one message per week, for up to three weeks. A recruitment flyer will be handed out or hung in clinic or sent via mail with the study invitation. For participants who contact the PI or research staff regarding participation via email or phone, research staff will respond in the same mode of contact. Participants will be paid \$20 for each interview or usability session completed.

For Phase 2, we will use the existing LITE program mailing list to mail invitational letters to all LITE parents and/or patients ages 13-25 informing them of the study. The LITE program maintains a clinical contact list to send periodic newsletters and mailings to patients. This letter will be written from [name], the patient's physician and Medical Director of the LITE program who has routine contact with these patients, and the PI of the study, to invite potential participants to contact the research team to ask questions or enroll in the study as well as inform potential participants of in-person informational meetings to be held by the PI and study team at Rutgers CINJ. We will follow-up by phone to answer any questions and determine interest in participating. Phone calls can be made up to three times per week, with a maximum of one message per week, for up to three weeks. We will arrange for in-person meetings to obtain informed consent/assent; if it is not possible to schedule, we will mail consent/assent forms, discuss via phone, and have participants return completed forms via mail. Initial invitations will include a post card that the recipient may return to indicate that they are not interested in the study and we will remove them from the mailing list. Because we will recruit in cohorts, we will hold informational meetings about four to six times per year. These meetings are to provide information about the study, answer any questions, and obtain consent/parental permission/assent to individuals ready to enroll. All materials will be submitted to the IRB for approval prior to use. Informed consent/parental permission and assent (for children 13-17) will be obtained prior to any study procedure. Participants will be given as much time as needed to read the consent/assent materials and ask any questions. If any participant turns 18 during the study period, the participant will be re-consented using the appropriate approved consent form as soon as possible. Participants will be paid \$20 for completion of each assessment, for a total of \$100. Any participant who completes all

assessments will be entered into a raffle to win a fitness gift basket, including items such as water bottles, healthy snacks, and fitness equipment (valued at \$150).

6. Study Parameters/Measures

Phase 1: App Development. We will interview participants individually or in small focus groups regarding desired content and functional features of the app. The PI or a trained research assistant will conduct interviews in person or via phone using a guide. Interviews will be recorded and transcribed by a member of the team for content analysis. Usability testing will involve assessment of satisfaction, ease of learning the app, and memorability of the app. Usability testing may be done in person or via telephone while the participant is interacting with the application online. At the time of accrual, a medical chart review will be conducted by trained study personnel to assess type of cancer, treatment history (surgery, chemotherapy, radiation therapy), time since treatment completion, and general demographic information (i.e., gender, age, race, and ethnicity).

Phase 2: Pilot RCT. All measures selected for this study have demonstrated adequate validity and reliability (see Table 1). With the exception of the demographic survey, all measures will be administered at baseline (Time 1), Time 3 (~3 months), Time 4 (~6 months), and Time 5 (~9 months). Only the muscular fitness tests, cardiorespiratory fitness test, body composition measures, accelerometry, and self-reported physical activity and sedentary behavior will be administered at Time 2 (~2 months). The *primary outcomes* are muscular fitness and cardiorespiratory fitness as measured by the 10-repetition max tests and submaximal treadmill testing (Aim 3). *Secondary outcomes* include health-related quality of life (HRQOL) and fatigue (Aim 4). We will also examine other constructs from Social Cognitive Theory, including exercise motivations, barriers to PA, body esteem, and psychological functioning. Finally, we will examine measures of physical activity (objectively measured via accelerometers or “actigraphs”), sleep, and anthropometric body measurements. Accelerometers have been extensively validated as measures of physical activity in children and adolescents.³⁹ Data regarding usage of the intervention app and electronic accelerometer will also be collected. Physical fitness measures are expected to take 40-45 minutes to complete plus the 7-days of actigraph wear during usual activities. Surveys are anticipated to take up to 45 minutes to complete. At the time of accrual, a medical chart review will be conducted by trained study personnel to assess cancer type, treatment history (surgery, chemotherapy, radiation therapy), time since treatment completion, and general demographic information (i.e., gender, age, race, and ethnicity).

Construct	Measure	Description	Type	Time to Complete
Muscle Strength	10-Repetition Max Test (Upper & Lower Body)	Primary Outcome ; Yields maximum resistance that can be lifted throughout the full range of motion using good form for 10 times for upper and lower body	O	15-20 min
Cardiorespiratory Fitness	Submaximal Treadmill Test ^{40,41}	Standardized graded treadmill test; yields estimated VO ₂ max	O	20 min
Health-Related Quality of Life	PedsQL Generic Core ^{42,43}	Physical, Emotional, Social, and Cognitive domains	P	5 min
Fatigue	PedsQL Multidimensional Fatigue Scale. ⁴⁴	Fatigue	P	5 min

“TLC FIT”: A Novel Mobile Health Fitness Program for Adolescent and Young Adult (AYA) Childhood Cancer Survivors
[name]

Physical Activity	Accelerometry (actigraph): 7-day activity	Objective measure of activity counts and time spent in sedentary, light, moderate, and vigorous activity	O	7-day wear
	FitBit Tracker physical activity data	Used as part of intervention, steps counts and time in various levels of activity will be collected weekly	O	---
	Modified International Physical Activity Questionnaire (IPAQ-SF) ⁴⁵	Self-reported physical activity within past 7 days	P	< 5 min
Sedentary Activity	Sedentary Habits Questionnaire	Sedentary habits within past 7 days	P	< 5 min
Body Composition	Height & Weight	Height & weight measurements	O	< 5 min
	Waist Circumference	Waist circumference	O	< 5 min
	BodPod ⁴⁶ [Optional for participants who agree]	The Bod Pod is a gold standard in body composition measurement. It is an air displacement plethysmograph which uses whole-body densitometry to determine body composition (fat and fat-free mass) in adults and children. This will be optional for participants who sign an additional consent for this test.	O	< 5 min
Barriers to PA	Barriers to Exercise Scale ⁴⁷	Barriers to PA	P	< 5 min
Exercise Motivation	Motivation for Exercise Item	Motivation for exercise	P	2 min
Psychological Symptoms	PROMIS Anxiety and PROMIS Depression measures ⁴⁸ – Pediatric and Adult forms depending on age	Symptoms of depression and anxiety	P	5 min
Body Esteem	Child & Youth Self-Perception Inventory ⁴⁹	Body self-esteem and overall self-esteem	P	10 min
Sleep Quality	Pittsburgh Sleep Quality Index ⁵⁰	Sleep quality	P	5 min
Demographics	Information Survey	Age, gender, race/ethnicity, socioeconomic status	P	< 5 min
Intervention Feedback	Feedback Questionnaire	Given after intervention to assess satisfaction and ideas for improving intervention	P	5 min

Note. Type of Measure: O = Objective; P = Patient-reported. The BodPod body composition test will be optional for participants who agree to it; evaluating changes in body composition is exploratory and will provide pilot data for future studies.

Table 2. Assessment Schedule

Measure	Time of Assessment				
	Baseline (0 Mo.)	Time 2 (~2 Mo)	Time 3 (~3-Mo)	Time 4 (~6-Mo)	Time 5 (~9-Mo)
10-Repetition Max (Upper & Lower)	√	√	√	√	√
Submaximal Treadmill Test	√	√	√	√	√
Height, Weight, Waist Circumference	√	√	√	√	√
BodPod body composition [optional]	√		√		√
Actigraphy	√	√	√	√	√
Demographic/Medical Information	√				
Modified IPAQ-SF	√	√	√	√	√
Sedentary Habits	√	√	√	√	√
Barriers to Exercise Scale	√		√	√	√
Motivation for Exercise Item	√		√	√	√
PedsQL: Generic Core	√		√	√	√
PedsQL: Multidimensional Fatigue Scale	√		√	√	√
PROMIS Anxiety & PROMIS Depression	√		√	√	√
Child & Youth Self-Perception Inventory	√		√	√	√
Pittsburgh Sleep Quality Index	√		√	√	√

Note. ^a For intervention group only; ^b For waitlist control group only. If individuals miss or need to reschedule assessments, they should be completed within 4 weeks of the scheduled time point.

7. Data Collection and Records to be Kept

7.1 Research Charts

Hard copies of data for each patient enrolled will be kept in a locked filing cabinet in the PI's locked office. Electronic files of interviews from Phase 1 will be downloaded from the recording device to a folder on the PI's secure departmental drive as soon as possible after the interview. It will then be erased from the recorder and only authorized study personnel will have access to the electronic files. Interviews will be transcribed as soon as possible and any identifying information will be removed in the written transcript. The electronic file will be destroyed at the end of study procedures (i.e., after transcription is complete and verified to be accurate by the PI). In Phase 2, patients will be registered for the trial using OnCore. All data (i.e., surveys, medical review sheet, fitness data) for each participant will be identified with an identification number rather than patient information and the key linking patient name and identification number will be kept locked in a separate file. Signed informed consent/permission and assent forms will also be kept in a locked cabinet separately from research files. Only authorized research personnel will have access to these files. We will also maintain an electronic database of potentially eligible patients we have contacted and track if any person returns a postcard asking to be removed from our contact list. This database will be stored on the PI's departmental drive and password protected. The key that links patient names and identification numbers will be destroyed after all procedures are complete and data is checked, by the close of the study.

7.2 Reports

Publications and annual reports for submission to the IRB will be written by the Cancer Institute of New Jersey PI using the data captured in the electronic database and the OnCore system.

8. Data and Safety Monitoring

The PI will convene a Data and Safety Monitoring Board (DSMB) composed of a behavioral scientist and a clinician to be named. The PI will conduct quarterly reviews of data and patient safety and send these reports to the DSMB for review. All unexpected and/or serious adverse events occurring during the active portion of the intervention or up to 30 days after the last fitness program session, will be reported to the Rutgers CINJ Office of Human Research Services and the IRB in accordance with IRB policy.

9. Statistical Considerations

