TLC FIT (Technology-Enhanced Intervention): TLF FIT is composed of the group fitness program, use of an electronic accelerometer, private Facebook group and the mobile app. The group fitness program is manualized and will be led by a qualified trainer. The PI will teach the trainer the manualized program and treatment integrity will be evaluated during the program. The group program has four primary components: (1) cancer-specific and general educational modules, (2) physical exercise, (3) goal-setting and self-monitoring, and (4) social support. The original program consisted of eight weekly group sessions; however, participants expressed interest in adding exercise sessions, which would likely increase the impact on participants’ fitness. Therefore, the program is now 8 weekly group sessions lasting 90 minutes each plus 4 weeks of using the app without in-person groups. In-person sessions will consist of approximately 20 minutes of education regarding fitness and administrative tasks, 10 minutes of goal-setting/monitoring, and 60 minutes of instructor-led exercise and cool-down (~30 minutes of aerobic exercise and 30 minutes of muscle strengthening and balance exercises). Exercises are age-appropriate and the intensity of participation is individualized – that is, any exercise can be modified to be more or less strenuous for each participant based on participants’ ratings of perceived exertion as well as any physical limitations due to cancer treatment (such as hip problems). The trainer will have experience in assisting teens and young adults in modifying exercises to a level appropriate to their current fitness and physical abilities. Participants will wear a commercially available electronic accelerometer daily throughout the intervention to self-monitor progress. Data from the accelerometer will be electronically extracted into the app for easy monitoring and sharing of goals/progress. Social support for physical activity will be fostered through group interactions at each session and group messaging within the app and Facebook private groups. During the follow-up period, participants continue to use the app, set physical activity goals, and monitor progress. We will remotely download data regarding app use weekly throughout the intervention and follow-up.

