Aim 3: This aim is to determine the effectiveness of the program on the primary outcomes, objectively-measured cardiorespiratory fitness and muscular fitness. The primary hypothesis is that participants in the intervention group will demonstrate greater improvement in cardiorespiratory fitness (measured via the Submaximal Treadmill test) and muscular fitness (measured via the objective 10-repetition max tests) from baseline than wait-list control participants at the 3-month assessment (after the intervention group completes TLC FIT). To test this hypothesis, the two groups’ outcome scores at the post assessment will be compared using ANCOVA, controlling for baseline scores. To account for enrollment in cohorts, cohort will be included as a covariate and removed if not significant. The primary analysis will be performed on an “intent-to-treat” basis; i.e., once a subject is randomized, data on that subject will be analyzed according to assignment, regardless of the degree to which the subject participates.

Aim 4: This aim will evaluate the effects of the program on the secondary outcomes of HRQOL and fatigue. We will test the hypothesis that participants in the intervention group will demonstrate greater improvement in HRQOL and fatigue from baseline than the wait-list control group at the 3-month assessment using ANCOVA.

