10.2 Potential Risks

Potential risks are considered minimal. In Phase 1, the risks are the same as encountered in daily life. The interviews will focus on app design and development and individuals' perceptions of its usefulness in daily life. In Phase 2, increased physical activity may result in muscle soreness or injury; however, each participant will be required to have their physician, oncologist, or physician's designee complete a form prior to enrollment clearing the participant for engagement in a physical activity program. Physical fitness testing will be done by trained personnel. [name], a mentor and Co-Investigator on this project, is a certified strength and conditioning specialist and will provide expert guidance to [name] for hiring and training qualified personnel. It should be noted that the fitness tests utilize standard exercise testing protocols. To protect the participants against risks of injury, the trainer will have adequate experience and training in working with AYAs, with a preference for certification in working with cancer survivors. All exercises will be age-appropriate and the intensity can be modified according to individual comfort. Further, the trainer will have each participants' emergency contact information with them during all sessions in the event that an injury occurs. Adolescents and young adults may feel uncomfortable answering

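### The only adverse-event rule is tied to the intervention, so on its natural reading it leaves out the wait-list arm up to Time 4 and most study fitness tests, and no other collection procedure is described

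*Combined protocol and SAP*

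**What the plan says.** Section 8 (Data and Safety Monitoring) has two provisions on safety. The first is a general review: "The PI will conduct quarterly reviews of data and patient safety and send these reports to the DSMB for review". It states no time window, arm or threshold of seriousness. The second governs reporting to the institutional research office and the IRB. It covers "All unexpected and/or serious adverse events" that fall in a window, namely those "occurring during the active portion of the intervention or up to 30 days after the last fitness program session".

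The timing of the intervention comes from sections 4.1 and 4.2. The programme is "8 weekly group sessions lasting 90 minutes each plus 4 weeks of using the app without in-person groups". For the control arm, "Individuals randomized to the waitlist will receive the intervention after the 6-month assessment". For the TLC FIT arm, exercise supported by the app carries on afterwards: "During the follow-up period, participants continue to use the app, set physical activity goals, and monitor progress".

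Table 2 schedules the 10-repetition maximum test and the submaximal treadmill test at all five time points. Section 4.1 adds a further fitness test for wait-list participants at their last in-person session. Table 2 has no adverse-event row. Section 10.2 names the physical risk of Phase 2: "increased physical activity may result in muscle soreness or injury".

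**The concern.** Both limits of the window are intervention events. A wait-list participant has neither an active intervention period nor a fitness session during the first six months, so an event in that time meets neither limit. Sections 9.1 and 9.4 place the between-group comparison at Time 3, about 3 months, which is entirely inside that gap.

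The study also imposes exertion of its own on both arms through repeated strength and treadmill tests, and many of these fall before the window opens or after it closes. Within the window the rule takes only unexpected or serious events, whereas soreness and minor injury are foreseen in section 10.2 and mostly non-serious.

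At stake is the usefulness of the pilot's safety data. Section 10.5 describes the risks as minimal and says the data will be used to refine procedures for a larger trial. If events are sought in one arm during its sessions and not in the other, a difference in counts between arms may reflect only who was asked.

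**Working it through.** The plan states no figure on this point, so there is none to reproduce. The check sets the section 8 window against the assessment schedule, participant by participant.

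**Inputs**
- Assessments at about 2, 3, 6 and 9 months after randomisation (section 4.2), with baseline tests before randomisation (section 9.3).
- Eight weekly sessions, then four weeks of app use alone, 12 weeks in all (section 4.1).
- Wait-list participants start after the 6-month assessment (section 4.2).
- One test occasion is the 10-repetition maximum plus the treadmill test: 5 in TLC FIT and 5 + 1 = 6 in the wait-list arm, 11 in total (Table 2; section 4.1).

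**Assumptions**
- A month is 30.4 days.
- TLC FIT sessions start at day 0, and wait-list sessions one day after Time 4.
- The last session is 49 or 56 days after sessions start.
- The active portion is either the sessions alone or the full 12 weeks (84 days).

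**Window**
End = start + the later of (end of active portion) and (last session + 30 days).
- Last session at day 49: 49 + 30 = 79, or 84 if the active portion is 12 weeks.
- Last session at day 56: 56 + 30 = 86, under either reading of active portion.
- TLC FIT: day 0 to day 79–86.
- Wait-list: start at 6 × 30.4 + 1 = 183.4; end at 183.4 + 79 = 262.4 to 183.4 + 86 = 269.4.

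**Test occasions against the window**

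| Occasion | Day | TLC FIT | Wait-list |
|---|---|---|---|
| Time 1 | before 0 | outside | outside |
| Time 2 | 2 × 30.4 = 60.8 | inside | outside |
| Time 3 | 3 × 30.4 = 91.2 | borderline, about 5 to 12 days late | outside |
| Time 4 | 6 × 30.4 = 182.4 | outside | outside |
| Wait-list last session | 183.4 + 49 or 56 = 232.4 or 239.4 | not applicable | inside |
| Time 5 | 9 × 30.4 = 273.6 | outside | borderline, about 4 to 11 days late |

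Clearly inside: 1 + 1 = 2. Borderline: 1 + 1 = 2. Clearly outside: 3 + 4 = 7. The share missed is therefore 7/11 = 64% if both borderline occasions count as inside, and 9/11 = 82% if neither does. The two readings of active portion give the same count.

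Table 2 lets a missed visit be made up within 4 weeks. At the limit, Time 2 in TLC FIT would move to 60.8 + 28 = 88.8, past the latest window end of 86.

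**Control arm during the comparison**
The wait-list window opens at about day 183 and the comparison is at about day 91. The overlap is 0 days.

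**The case against.** Several objections are sound and limit the point.

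- **The windowed sentence is about reporting to the institutional office and the IRB, not about the DSMB.** This stands. A reader might infer that events at test visits would not reach the DSMB. The documents do not support that, since the quarterly review has no stated window and could include them. What is missing is any described procedure for collecting them.
- **The window may not be meant per participant.** Section 8 names no arm, does not define the active portion, and does not say whose last session counts. If it ran on the cohort's calendar to the last wait-list session plus 30 days, controls would be covered and that part of the point would fail. Baseline tests would still precede it. The per-participant reading is the natural one, but zero control coverage follows from that reading and is not stated in the text.
- **Both arms are seen.** This stands. Everyone attends the same five assessments with trained staff, and wait-list participants enter the window once they start the programme. It would be wrong to say that only one arm is observed. But Table 2 gives staff at those visits no adverse-event item to complete.
- **No aim concerns comparative safety.** True. Section 9.2 puts the focus on feasibility and effect size, section 10.2 requires medical clearance and trained testers, and section 2.1 reports no serious adverse events among nine preliminary participants. The plan does not fail an aim. The pilot will nevertheless produce safety data, and these should be gathered alike in both arms.
- **IRB policy may require more.** Possibly, but that policy is not in the documents and cannot be relied on here.

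**Conclusion.** The point holds. The one adverse-event rule is anchored to the intervention, and no collection procedure is set out for controls, for study-mandated tests or for non-serious injury. Read per participant, the wait-list arm is uncovered from baseline to Time 4, including the whole 3-month comparison, and 7 of 11 test occasions are clearly outside the window, with 2 more borderline. The consequence is unequal ascertainment in any adverse-event count by arm.

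The test-occasion count rests on nominal visit times and on sessions starting promptly after randomisation (TLC FIT) or Time 4 (wait-list). A later start would bring the borderline visits inside. The control-arm gap rests only on the per-participant reading. The efficacy analysis is not affected. The stronger conclusions, that the DSMB would be kept from these events or that controls are not observed at all, go beyond the text.

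**What to change.** Amend section 8 and Table 2 as follows.

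- Add an adverse-event row to Table 2: the same question, in both arms, at every existing assessment from the baseline fitness test to Time 5. Include non-serious injuries related to exercise or testing. Since assessors are masked (section 9.3), ask it after the fitness tests so that an answer cannot reveal the arm before the tests are scored.
- State in section 8 that the window applies to both arms and to study-mandated tests. Define the active portion and say whose last session is meant.
- Tabulate events by arm from baseline to Time 3 and from baseline to Time 4, and include the table in the quarterly DSMB report.

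Reporting to the institutional office and the IRB continues under IRB policy. The cost is a small amount of staff time at visits that already take place, and one extra table.
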